The aim of this study is therefore to highlight the effects of fasciatherapy on low back pain through an assessment of pain, quality of life, functionality and anxiety. It also aims to observe how fasciatherapy could contribute to the management of low back pain in the context of massage and physiotherapy.

This is a randomised cluster study with pain as the primary endpoint, involving 180 participants. The evaluation criteria include pain assessment using the Visual Analogue Scale (VAS), functional assessment using the Dallas Pain Questionnaire, quality of life evaluation with the SF-12 questionnaire, psychological assessment of anxiety using the STAI, and monitoring of medication use based on information provided by patients to the practitioner.

The practical conduct of the study is structured as follows:

- Recruitment of physiotherapists (investigators) by the FasciaFrance association and verification via their Curriculum Vitae of the investigators' inclusion criteria,
- Randomization of investigators into three groups based on the care they will provide: massage-physiotherapy care, combined massage-physiotherapy and fasciatherapy care, and fasciatherapy-only care.,
- Distribution of the investigator's brochure and observation booklet,
- Each investigator recruits their patients and adheres to the protocols outlined in the investigator's guide and observation booklet.
- Submission of anonymized ("coded") data by the investigators to the study sponsor.
- Data entry in the ACCESS database,
- Statistical analysis of the data using STATA software,
- Publication of the results.

CONTENTS

1	Gen	eral information	6	
	1.1	Title of research	6	
	1.2	Coordination and monitoring of the study - promoter	6	
	1.3	Coordinating investigator	6	
	1.4	Co-investigator - scientific collaborator - investigator - statisticians and associate partn	er 6	
	1.5	Study locations	7	
	1.6	Study timetable	7	
2	Stuc	ly rationale and scientific justification	7	
3	Aim	s of the study	9	
	3.1	Main objective	9	
	3.2	Secondary objectives	9	
4	Stuc	ly category	9	
	4.1	Search category	9	
	4.2	Justification for qualification	9	
5	Pop	Population studied / concerned		
	5.1	Inclusion criteria	9	
	5.2	Non-inclusion criteria	9	
	5.3	Procedure for early termination of research	10	
	5.4	Recruitment procedures	10	
6	Des	cription of the study	10	
	6.1	Assessment criteria	10	
	6.1.	Primary endpoint	10	
	6.1.2	2 Secondary evaluation criteria	10	
	6.2	Investigation method used	10	

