6.3 Description of measures taken to reduce and avoid bias

Cluster randomised trial :

- Practitioners will be randomly assigned to one of the three study groups.
- All patients of the same practitioner will be assigned to the same randomisation group.
- Randomisation will be carried out in blocks of random size.

For the duration of the study, the practitioner undertakes to offer all patients eligible for inclusion the opportunity to take part in the study.

The multicentre nature of the study will minimise the practitioner effect inherent in this type of clinical research.

The self-administered questionnaires will be given to the patient in person, and the patient will be left alone while the questionnaire is completed.

Only the analysis of the data will be unblinded. In addition, the data will be anonymised to guarantee confidentiality.

7 Duration and organisation of the research

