7.3 Description of the general logistical organisation of the trial

Practitioners will receive an observation booklet by post. Each practitioner will include between 3 and 5 patients in the study.

The promoter is responsible for gathering all the data collected at each phase of the study and at the end of the study. They will compile the data into an Excel file and transmit it to the statistician.

- 7.4 Inclusion criteria for practitioners
 - Qualified physiotherapist,
 - Private practice,
 - Having a mixed practice combining conventional physiotherapy and fasciatherapy which is outside the scope of conventional practice,
 - Having completed at least 105 hours of training in fasciatherapy.

8 Data collected

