8.3.4 Archiving

The following documents will be archived by the name of the study at the FasciaFrance premises, under the responsibility of the coordinating investigator and FasciaFrance for 15 years after the end of the study.

These documents are :

- Protocol, observation book, any amendments,
- Original signed information forms and consents
- Individual data (authenticated copies of raw data)
- Follow-up documents
- Statistical analysis
- Final study report

At the end of the period of practical use, all documents to be archived will be placed under the responsibility of FasciaFrance.

No removal or destruction may be carried out without the agreement of the Developer. At the end of the 15 years, the Promoter will be consulted for destruction. All data, documents and reports may be subject to audit or inspection.

9 Statistical considerations

- 9.1 Data analysis method
 - 9.1.1 General

Statistical analysis will be carried out using Stata software (version 15, StataCorp, College Station).

Continuous variables will be presented in the form of mean and standard deviation, subject to the normality of their distribution (Shapiro-Wilk test if necessary). In the event of non-normality, they will be presented in the form of median, quartiles and extreme values. Qualitative variables should be expressed in terms of numbers and associated percentages. Wherever possible, graphical representations should be associated with these analyses.

Patients will be described and compared between groups (group receiving conventional physiotherapy only, group receiving both conventional physiotherapy and fasciatherapy and group receiving fasciatherapy only) at inclusion according to the following variables: compliance with eligibility criteria, epidemiological characteristics, clinical characteristics and characteristics of any treatments.

A description of protocol deviations, patients allocated according to these deviations and reasons for drop-out will also be provided. The number of patients included and the inclusion curve will be presented by randomisation group.

The initial comparability of the groups will be assessed on the main characteristics of the participants and potential factors associated with the primary endpoint. Any difference between groups on any of these characteristics will be determined on the basis of clinical and not just statistical considerations.

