Comparisons between randomisation groups will be made systematically (1) without adjustment (2) by adjusting for factors whose distribution could be unbalanced between groups.

All statistical tests will be carried out with a risk of error of the first kind α of 5%.

Part of the analyses concerning the secondary evaluation criteria should be mainly exploratory in nature. As discussed by several authors (*Bender, R.; Lange, S. Adjusting for multiple testing-When and how? J. Clin. Epidemiol. 2001, 54, 343-349; Feise, R.J. Do multiple outcome measures require p-value adjustment? BMC Med. Res. Methodol. 2002, 2, 8; Rothman, K.J. No adjustments are needed for multiple comparisons. Epidemiology 1990, 1, 43-46*), adjustment for the risk of error of 1st kind will not be proposed systematically, but on a case-by-case basis in the light of clinical and not purely statistical considerations.

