9.1.2 Main analysis

In order to evaluate the specific benefits of fasciatherapy compared with physiotherapy for chronic low back pain in terms of variation in pain before and after each of the 5 sessions considered in this protocol, the main analysis will consider a mixed model approach for repeated data, making it possible to study the fixed group effects (group receiving only conventional physiotherapy, group receiving both conventional physiotherapy and fasciatherapy and group receiving fasciatherapy only), assessment time (session) and their interaction, while taking into account inter- and intrapatient variability (subject taken as a random effect), in addition to the (random) practitioner effect. The results will be expressed in terms of regression coefficient and 95% confidence interval. It will also be proposed to study the difference between randomisation groups for each of the sessions. The results will be expressed in terms of effect size and 95% confidence interval.

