9.1.4 Method for taking into account missing, unused or invalid data

A sensitivity analysis will be carried out to study the attrition bias, i.e. the quantity (level of attrition) and nature (independence from the randomisation group) of the missing data, and to propose the most appropriate data imputation method if necessary.

9.2 Justification of the number of subjects / power analysis.

In order to evaluate the specific benefits of fasciatherapy compared with physiotherapy for chronic low back pain in terms of variation in pain before and after each of the 5 sessions considered in this protocol, the estimate of numbers is based on recruitment capacity, the time required for experimentation and simulations concerning the effect size for risks of error of 1st and 2nd kind fixed respectively at 1.7% (two-sided with correction for multiple comparisons: group receiving only conventional physiotherapy, group receiving conventional physiotherapy and fasciatherapy) and less than 20%.

Thus, if we estimate that a clinically relevant difference in pain assessment is between 1 and 2 points, for a standard deviation of the variation in pain of 1.5 to 2.5 points, we should include 30 to 40 patients for a statistical power of over 80% and an intra-individual correlation coefficient (5 sessions per subject) conventionally set at 0.5.

This proposal must be revised upwards in order to take into account the dropouts inherent in this type of protocol and the inter- and intra-practitioner variability (due to the experimental design of the cluster trial) which can be measured by the intra-class correlation coefficient and which it seems reasonable to estimate in the context of this project to be of the order of 0.05 to 0.2. It is therefore proposed to include 60 patients in each of the study groups.

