11.4 Feasibility of the study

- Competencies of the teams involved: All practitioners have a state diploma in massophysiotherapy and must practice fasciatherapy (with a training course of at least 105 hours).
- Recruitment possibilities: A preliminary questionnaire distributed to members of Fascia France showed that 49 practitioners were willing to participate in the study. Of these, 41 could include patients with low back pain. The total number of potential patients for inclusion ranged between 200 and 370.
- Sessions take place in the practitioner's office, which is the one the patients have contacted.

12 Financing and insurance

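### The primary group contrast rests on about 36 to 49 randomised practitioners, and the plan names no small-sample method of inference for it

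*Combined protocol and SAP*

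**What the plan says.** Section 6.3 makes the practitioner the unit of randomisation: "Practitioners will be randomly assigned to one of the three study groups". All patients of one practitioner are in the same group. The summary describes a trial "involving 180 participants", and section 9.2 proposes to "include 60 patients in each of the study groups". Section 7.3 sets the cluster size: "Each practitioner will include between 3 and 5 patients in the study". Section 11.4 reports the supply of practitioners: "49 practitioners were willing to participate in the study. Of these, 41 could include patients with low back pain".

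The main analysis in section 9.1.2 is a mixed model for repeated pain changes. It has fixed effects of group, session and their interaction, and a random subject effect "in addition to the (random) practitioner effect". Results are regression coefficients with 95% confidence intervals, and group differences at each session are also studied. Section 9.1.3 uses the same structure for the repeated anxiety score and keeps the random practitioner effect in the covariate-adjusted model.

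Section 9.1.1 names Stata 15 without a command or option, and sets tests at 5%. Nowhere does the plan mention restricted likelihood, a degrees-of-freedom method, a t or F reference, or a permutation test. It also does not say that maximum likelihood or z-tests will be used.

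**The concern.** The random practitioner effect is the right model term, but it does not by itself give valid inference when practitioners are few. The 180 patients give 180 × 5 = 900 pain changes, which looks like a large sample. For the contrast between groups, however, the information is limited by the number of practitioners. Two things then go wrong under ordinary large-sample inference. Maximum likelihood takes no account of the fixed group effects when it estimates the variance between practitioners, so the standard error is too small. A normal critical value ignores the fact that this variance is itself estimated.

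What is at stake is the confidence interval and p-value of the primary comparison. Maximum likelihood with z, restricted likelihood with z, and restricted likelihood with t all fit the plan as written, and they give different intervals. Leaving the choice open until the data are in is a gap in pre-specification, even though the differences are modest.

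**Working it through.** The plan gives no test size or degrees of freedom to reproduce. Its 60 per group agrees with the total (3 × 60 = 180). One route to 60 is 30 × (1 + 4 × 0.2) / 0.9 = 60, with 5 patients per practitioner, an intraclass correlation of 0.2 and an assumed 10% dropout. The plan states no dropout rate, so this route is not unique, and nothing below depends on it.

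**Number of randomised units, K.** Cluster sizes of 3 to 5 give 180/5 = 36 to 180/3 = 60. Section 11.4 offers 41 practitioners able to include patients, from 49 willing (180/41 = 4.4 and 180/49 = 3.7 patients each). The realistic range is therefore K = 36 to 49, or 12 to about 16 per arm. With three arms, the degrees of freedom are K − 3 = 33 to 46.

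**Analytic size, session-averaged pairwise contrast, balanced design, nominal two-sided 5%.**
- Restricted likelihood with z: 2 × P(t[K−3] > 1.960).
- Maximum likelihood with z: the standard error is too small by √((K−3)/K), so the size is 2 × P(t[K−3] > 1.960 × √((K−3)/K)).

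| K | df | Effective cut-off under ML | Size, ML with z | Size, REML with z | Correct t critical value |
|---|---|---|---|---|---|
| 36 | 33 | 1.877 | 6.95% | 5.85% | 2.035 |
| 41 | 38 | 1.887 | 6.7% | 5.7% | 2.024 |
| 49 | 46 | 1.899 | 6.4% | 5.6% | 2.013 |

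The 2-df test of any group difference, referred to chi-square, is further from nominal: 7.9%, 7.5% and 7.0% with maximum likelihood, and 6.4%, 6.2% and 6.0% with restricted likelihood.

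**Simulation.** 400,000 null trials per scenario were run with five sessions, the plan's intra-individual correlation of 0.5 and its practitioner intraclass correlation of 0.05 to 0.2 (section 9.2). Clusters were equal, data were complete, and negative variance estimates were set to zero. K was 36, 45 and 60. K = 49 was not run; it lies between the last two rows.

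| K | Session-averaged, ML z | REML z | REML t | Session-specific, ML z | REML z |
|---|---|---|---|---|---|
| 36 | 6.5–7.0% | 5.6–5.8% | 4.8–5.0% | 5.9–6.4% | 5.2–5.5% |
| 45 | 6.2–6.5% | 5.5–5.7% | 4.8–5.0% | 5.7–6.0% | 5.1–5.3% |
| 60 | 5.8–6.1% | 5.3–5.5% | 4.8–5.1% | 5.5–5.7% | 5.1–5.2% |

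Session-specific contrasts are less affected because part of their variance is within-patient residual, which is estimated on (180 − 3) × (5 − 1) = 708 degrees of freedom. The interaction test, with (3 − 1) × (5 − 1) = 8 degrees of freedom, is judged on that residual alone. Its size is about 5.6% even with maximum likelihood.

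**Width of the 95% interval after correction.** Against restricted likelihood with z, the ratio of critical values is 2.035/1.960 = 1.038 at K = 36 and 2.013/1.960 = 1.027 at K = 49, so 3 to 4% wider. Against maximum likelihood with z, multiply by √(K/(K−3)): 1.038 × √(36/33) = 1.084 and 1.027 × √(49/46) = 1.060, so 6 to 8% wider.

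**The case against.** The strongest reply is that this is an omission and no stated rule is wrong. The plan already treats practitioner as random. Section 9.3 refers to a statistical analysis plan with successive versions, where estimation options could be set. That stands. A reader might infer that the plan prescribes maximum likelihood with z-tests, so that the primary intervals must be too favourable. The documents do not say so, and every size above 5% given here is conditional on that choice.

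A second reply is that the largest figures belong to the contrast averaged over sessions, whereas section 9.1.2 includes the interaction and also studies each session. Under ordinary reference coding the group coefficient is itself a session-specific difference. This also stands, and is why both sets of figures are shown.

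Two further inferences should be resisted. One is that the type I error is close to double the planned level. At the 1.7% level, maximum likelihood with z gives 2.9% at K = 36, about 1.7 times nominal, and restricted likelihood with z gives 2.3%. But 1.7% appears only in the sample-size argument of section 9.2, while section 9.1.1 tests at 5%, where the worst pairwise ratio is about 1.4 (6.95/5). The other is that as many as 60 practitioners might take part; that is only 180/3 and exceeds the supply in section 11.4.

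What the reply does not remove is that nothing in the document rules out large-sample inference for a contrast with 33 to 46 degrees of freedom.

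**Conclusion.** The point holds as a conditional one. If the model in section 9.1.2 is fitted with large-sample inference, pairwise tests of the session-averaged group contrast run at about 6 to 7% (maximum likelihood) or 5.4 to 5.8% (restricted likelihood) instead of 5%. Nominal 95% intervals then cover about 93 to 94% or 94.2 to 94.6%. Session-specific contrasts run at about 5.6 to 6.4% and 5.1 to 5.5%, and the interaction is little affected. Restricted likelihood alone removes only part of the excess; with a t reference on K − 3 degrees of freedom, the simulated size is 4.8 to 5.0% at K = 36 and 45.

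These figures assume 36 to 49 practitioners, a roughly equal split over arms, equal clusters, complete data, and the correlations in section 9.2. Uneven recruitment or dropout would probably enlarge the excess, but this was not simulated. The matter is minor to moderate: it would not overturn a clear result, but it could move a borderline one.

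**What to change.** Add to section 9.1.2, and apply to the linear mixed models in section 9.1.3: 'Linear mixed models will be fitted by restricted maximum likelihood with Kenward-Roger (or Satterthwaite) degrees of freedom for group contrasts; the number of practitioners analysed per arm will be reported.' Choose one of the two methods before the data are analysed. Both set the degrees of freedom contrast by contrast, so session-specific differences are not over-corrected. A t or F reference on practitioners minus arms is a simple fallback for the session-averaged contrast.

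The cost is one sentence and one option in the analysis program, with no new data and no change of design. Section 9.3 allows the analysis plan to be revised. The 95% intervals become about 3 to 4% wider than with restricted likelihood and z, or about 6 to 8% wider than with maximum likelihood and z. The sentence does not cover the logistic mixed models in section 9.1.3, which would need their own statement.

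### Section 9.1.2 does not name the primary contrast from the group-by-session model, and the 5% test level in 9.1.1 does not match the 1.7% used for sizing in 9.2

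*Combined protocol and SAP*

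**What the plan says.** Section 9.1.2 concerns the change in pain from before to after each of the five sessions. The mixed model has fixed effects for group (three levels), session and their interaction, and random effects for patient and practitioner. On reporting it says: "The results will be expressed in terms of regression coefficient and 95% confidence interval". It then adds: "It will also be proposed to study the difference between randomisation groups for each of the sessions", given as effect sizes with 95% confidence intervals. It does not state the coding of group or session, whether session is categorical or linear, or any average over sessions. Section 6.1.1 defines the endpoint as VAS pain around each session and names no summary across sessions.

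Section 9.2 sizes the trial at "1.7% (two-sided with correction for multiple comparisons", with power above 80%. It takes a "clinically relevant difference in pain assessment is between 1 and 2 points", a "standard deviation of the variation in pain of 1.5 to 2.5 points" and "an intra-individual correlation coefficient (5 sessions per subject) conventionally set at 0.5". The result is 30 to 40 patients, raised to 60 per group for dropout and practitioner clustering.

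The general rules in 9.1.1 say: "All statistical tests will be carried out with a risk of error of the first kind" of 5%. The case-by-case approach to multiplicity in the same section is written for the secondary criteria.

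**The concern.** The model yields several possible answers to whether fasciatherapy reduces pain: the difference at one session, the difference averaged over five sessions, the way the difference changes across sessions, and five separate session differences. These estimate different quantities with different precision. If the plan does not choose, the meaning of the main result depends on a software coding default or on a choice made after the data are seen. The reported coefficient may then not be the effect the trial was sized for.

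The test level adds to this. Three groups give three pairwise comparisons. Section 9.2 corrects for multiple comparisons, but the section that governs testing does not. Neither section addresses multiplicity over sessions.

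**Working it through.** **Inputs.** From 9.2: difference 1 to 2 points, SD 1.5 to 2.5, two-sided level 1.7%, power 80%, five sessions, within-patient correlation 0.5, 60 per group. Critical values: z(1 − 0.017/2) = 2.387 and z(0.80) = 0.842.

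**Variance factors relative to one session (V).**
- Mean of five sessions: V = (1 + 4 × 0.5)/5 = 0.6.
- One session, such as the session-1 difference: V = 1.
- Session 5 minus session 1 (an interaction coefficient): V = 2 × (1 − 0.5) = 1.
- Ratio of one session to the mean: 1/0.6 = 1.67.

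**The plan's own figure.** n per group = 2 × (2.387 + 0.842)² × (SD/difference)² × V = 20.84 × (SD/difference)² × V.

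| Difference / SD | n, five-session mean | n, one session |
|---|---|---|
| 1 / 1.5 | 29 | 47 |
| 1 / 2 | 51 | 84 |
| 1 / 2.5 | 79 | 131 |
| 1.5 / 2 | 23 | 38 |
| 1.5 / 2.5 | 35 | 58 |
| 2 / 2.5 | 20 | 33 |

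The stated 30 to 40 agrees with the five-session mean at 1/1.5 and 1.5/2.5. It also agrees with one session at 1.5/2 and 2/2.5. Section 9.2 gives no specific pair, so the figure cannot be reproduced uniquely.

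**Power at 60 per group, no clustering.** Power = Φ(difference / √(2 × SD² × V/60) − 2.387).
- 1/2, mean: √(2 × 4 × 0.6/60) = 0.283; 1/0.283 = 3.536; Φ(1.149) = 87.5%.
- 1/2, one session: √(2 × 4/60) = 0.365; 1/0.365 = 2.739; Φ(0.352) = 64%.
- Other pairs, mean then one session: 1/1.5, 99% and 90%; 1.5/2, 99.8% and 96%; 1.5/2.5, 97% and 82%; 2/2.5, 99.9% and 98%; 1/2.5, 67% and 42%.

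**With clustering, as an illustration.** Take 4 patients per practitioner (section 7.3 allows 3 to 5) and ICC 0.1 (9.2 gives 0.05 to 0.2), and apply the same design effect to both contrasts. The design effect is 1 + 3 × 0.1 = 1.3, so the effective n is 60/1.3 = 46.2. Power for 1/2 is then 76% for the mean and 51% for one session. For 1/1.5 it is 96% and 79%.

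**What the coefficient would estimate.** Suppose the true average difference is 1.0.
- Growing over sessions (0.2, 0.6, 1.0, 1.4, 1.8): the reference-coded group coefficient is 0.2.
- Fading in the reverse order: it is 1.8.
- Constant: it is 1.0.
- Sum-to-zero coding: the group coefficient is 1.0 in all three cases.

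**False-positive risk if any significant result counted as success.** Simulated with no true effect, correlation 0.5 between sessions, no clustering and 400,000 draws.

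| Rule | Each test at 5% | Each test at 1.7% |
|---|---|---|
| Averaged contrast, any of three pairs | 12% | 4.4% |
| Any of five sessions, one pair | 18% | 7% |
| Any of five sessions, any of three pairs | 39% | 17% |

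**The case against.** Several stronger readings are tempting, and the documents do not support them.

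- *No coefficient in this model can be the five-session effect.* This depends on coding, which the plan leaves open. With sum-to-zero coding, or with session linear and centred and balanced data, the group coefficient is, or estimates, the average. The wording on regression coefficients is a reporting format, used again in 9.1.3, and does not nominate one coefficient.
- *The trial was sized on the five-session mean.* This is the natural reading, because the number of sessions and their correlation matter only if sessions are combined. Section 9.2 does not say so, and 30 to 40 also fits a one-session contrast for some pairs.
- *The main result would have less power than the plan claims.* At 60 per arm without clustering, one-session power is 82% to 98% for four of the six pairs above. It falls below 80% for 1/2 and 1/2.5, and those pairs need 51 and 79 per group even for the average. What holds generally is lower power than the average has.
- *The plan tests at each session and so carries an 18% or 39% false-positive risk.* Section 9.1.2 proposes per-session differences in addition to the model, as effect sizes with intervals. No rule makes any significant session a success, so these figures are conditional on such a rule.

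The equal-weight average is also not the only defensible target. The main objective in 3.1, the benefit of five sessions, could mean a cumulative or last-session effect.

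What stands is that no primary contrast is named anywhere, and that the test level in 9.1.1 differs from the one in 9.2. If the meaning of the main result turns on unstated coding, the result is not prespecified.

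**Conclusion.** The point holds as a gap in specification. Section 9.1.2 does not identify the primary contrast. Under categorical session and reference coding (assumed here as the usual software default), the group coefficient is the session-1 difference, with 1.67 times the variance of the five-session mean. The cost in power depends on the pair: about 24 points at 1/2, about 25 at 1/2.5, and between 2 and 15 points for the other four pairs. If the group difference is the same at every session, the estimate targets the same value and only precision is lost.

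The mismatch between 5% and 1.7% is in the text whatever the coding. Its consequence, about 12% over three pairs for the averaged contrast, assumes that any significant pair would be claimed as success. None of this shows that 60 per group is wrong. It should be corrected before analysis.

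**What to change.** 1. In 9.1.2, name as primary the group difference in before-after pain change, averaged with equal weight over the five sessions and obtained as a linear combination of model terms. This does not depend on the coding. State it for each pairwise comparison covered by the 1.7% correction and test it at 1.7%. Since 5%/3 = 1.67%, three comparisons appear to be intended, but the parenthesis in 9.2 lists only two of the groups, so the comparisons should be listed explicitly.
2. State whether session is categorical.
3. Amend 9.1.1 so that the 5% level does not govern these comparisons.
4. Label the interaction and the per-session differences as descriptive.
5. State in 9.2 that the sample size refers to this contrast, and give the difference and SD used.

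The cost is a few sentences and one post-estimation command, with no new data. The drawback is that an equal-weight average may dilute an effect that appears only in late sessions. The descriptive per-session results would still show it. If the sponsor prefers a last-session target, that contrast can be named instead, with 9.2 recalculated for it.

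### Section 9.1.2 compares the groups on pain at each of five sessions with no error control over sessions: even at 1.7% per pair, a null trial has about a 12–17% chance of a significant session

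*Combined protocol and SAP*

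**What the plan says.** - **Endpoint (6.1.1).** The primary endpoint is pain on the VAS before and after each session. There are five sessions.
- **Main analysis (9.1.2).** A mixed model has fixed effects for group, session and their interaction, and random effects for patient and practitioner. The section then adds: "It will also be proposed to study the difference between randomisation groups for each of the sessions". On reporting it says: "The results will be expressed in terms of effect size and 95% confidence interval". It does not say whether the group effect, the interaction, one pair of groups or one session decides the trial, and the session comparisons do not depend on any earlier result.
- **Test level (9.1.1).** "All statistical tests will be carried out with a risk of error of the first kind α of 5" per cent.
- **Multiplicity policy (9.1.1).** "Part of the analyses concerning the secondary evaluation criteria should be mainly exploratory in nature". The same paragraph says that "adjustment for the risk of error of 1st kind will not be proposed systematically, but on a case-by-case basis".
- **Sample size (9.2).** The type I error is "1.7% (two-sided with correction for multiple comparisons: group receiving only conventional physiotherapy, group receiving conventional physiotherapy and fasciatherapy". The five sessions appear there only as repeated measures with a correlation of 0.5.
- **Groups (6.3).** "Practitioners will be randomly assigned to one of the three study groups".

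**The concern.** The session comparisons concern the primary endpoint and stand in the section that defines the main analysis. The exploratory wording in 9.1.1 is about secondary criteria, so it does not cover them. The case-by-case clause commits to nothing. The 1.7% level is explained by groups and appears only in the sample-size section.

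A 95% interval that excludes zero is a 5% test, whatever it is called. As written, the plan leaves room to report a benefit on pain at, say, the third session when the groups do not differ over the five sessions as a whole. Nothing in the text would mark that as a supportive result.

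This gap is separate from the correction over the three arms. Carrying 1.7% into 9.1.2 would settle the arms and leave the sessions open.

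**Working it through.** **1. The plan's own figure.** Three groups give 3 pairs, and 5%/3 = 1.67%, which rounds to the stated 1.7%. Two comparisons would give 5%/2 = 2.5%, which does not match. So 1.7% is used up by the pairs of groups.

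**2. How 9.2 treats sessions.** The mean of five sessions with correlation 0.5 has variance factor (1 + 4 × 0.5)/5 = 0.6. Per group, n = 2 × (2.387 + 0.842)² × (SD/difference)² × 0.6.
- Difference 1, SD 1.5: 29 patients.
- Difference 1.5, SD 2.5: 35 patients.

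Both are consistent with the plan's 30 to 40, although the full stated ranges of difference and SD run from 8 to 79. The sizing therefore fits one averaged contrast per pair and makes no allowance for five separate tests.

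**3. Number of tests.** 3 pairs × 5 sessions = 15, or 2 × 5 = 10 if only the comparisons with physiotherapy are made.

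**4. Between-session correlation of group means.** The start is 0.5 (9.2). A practitioner effect shared by all sessions raises it. With m = 3 to 5 patients per practitioner (7.3) and ICC = 0.05 to 0.2 (9.2):
- If the 0.5 includes the practitioner effect: (0.5 + (m − 1) × ICC)/(1 + (m − 1) × ICC). For m = 3, ICC = 0.05: 0.6/1.1 = 0.545. For m = 5, ICC = 0.2: 1.3/1.8 = 0.722.
- If the 0.5 holds within practitioner: (ICC + 0.5 × (1 − ICC) + (m − 1) × ICC)/(1 + (m − 1) × ICC). For m = 5, ICC = 0.2: (0.2 + 0.4 + 0.8)/1.8 = 0.778.

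**5. Error rates with no group difference.** Simulation of null trials with three equal arms, five sessions, exchangeable correlation and normal statistics with known variance. Entries are the chance of at least one significant session comparison. The last column is the chance that some session is significant for some pair while none of the three five-session contrasts is.

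| Correlation | 15 tests, 5% | 15 tests, 1.7% | 10 tests, 5% | 10 tests, 1.7% | Session but no five-session contrast, 1.7% |
|---|---|---|---|---|---|
| 0.50 | 39% | 17% | 31% | 12% | 13% |
| 0.545 | 38% | 16% | 30% | 12% | 12% |
| 0.65 | 34% | 15% | 27% | 11% | 10% |
| 0.778 | 29% | 12% | 23% | 9% | 8% |

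For comparison, the three five-session contrasts alone give about 12% at 5% and 4.4% at 5%/3. One three-group test per session, at correlation 0.5, gives about 19% at 5% and 7% at 1.7%.

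**6. Share due to sessions.** At 1.7%, the rise from about 4.4% to 12–17% comes from the sessions. At 5%, the rise is from about 12% to 29–39%; the starting 12% belongs to the uncorrected pairs.

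**7. Error of the remedy.** The rule tests a pair's sessions only if its five-session contrast is significant at 1.7%, then applies Holm over the five sessions at that level. Under the global null at correlation 0.5 it gives about 2%. The gate without Holm gives 4.1%.

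**The case against.** The strongest reply is that the text describes estimation. The session comparisons are introduced as an addition, are reported as effect sizes with intervals, and have no decision rule or claim attached. The 5% in 9.1.1 is a level per test and makes no promise about a family of tests. This stands in part: nothing shows that the sponsor intends to claim benefit from a single session, and a reader who infers that goes beyond the documents. But the plan does not call these comparisons supportive either, and it fixes no primary contrast against which they would be secondary.

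A second reply concerns size. A reader might take 39% as the error caused by the sessions. The documents do not support that. The figure includes the uncorrected arms, needs all 15 pairwise tests, and needs a correlation of exactly 0.5 with no contribution from practitioners. The stated aim in 9.1.2, fasciatherapy against physiotherapy, could mean 10 tests, and the wording also fits one three-group test per session. Every one of these readings still exceeds 5%.

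A third reply is that the gate and Holm together are stricter than needed under the global null, where either alone gives about 4.1% at correlation 0.5. That is true. They guard against different cases: the gate protects when a pair's average difference is zero, and Holm protects when it is not but some sessions have no effect.

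**Conclusion.** The point holds: no rule in the plan limits error over the five sessions for the primary endpoint. With the 1.7% level applied to pairs, the chance of a false session finding is about 12–17% for three pairs and 9–12% for two, against about 4.4% for the three averaged contrasts. In about 8–13% of null trials a session would be significant at 1.7% with no five-session contrast to support it.

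These figures assume exchangeable correlation between 0.5 and 0.78, equal arms, a correctly modelled practitioner effect and large-sample normal tests. The 29–39% at 5% is correct for 15 tests as the plan is written, but it should be cited only as the joint effect of uncorrected arms and sessions. The gap should be closed. It does not invalidate the mixed model or the design.

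**What to change.** Replace the sentence on session differences in 9.1.2 with:

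> Differences between groups at each session are supportive. For each pair of groups, the five-session contrast is the model-estimated group difference in pain variation averaged over the five sessions, tested at 1.7% (5%/3) two-sided. Session differences for a pair will be tested only if that contrast is significant, with Holm adjustment over the five sessions at the same level. Otherwise they will be shown as estimates with confidence intervals and no claim of benefit.

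The contrast and its level must be written out because 9.1.2 defines neither. Each pair's session claims are then held to 5%/3, so the three pairs together stay within 5%.

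Report the sessions for state anxiety as supportive in the same way, since 9.1.3 gives that measure the same analysis as the primary endpoint. Section 9.1.3 calls the per-session measure STAI YB, while 6.1.2 assigns per-session completion to STAI YA; the two must be reconciled.

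The cost is wording only, with no extra patients or data, and section 9.3 already allows the SAP to be revised. The price is that an effect confined to one session can no longer be claimed on its own, though it would still be shown, and that the rule is conservative when no group differs.
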